7.2. Methods for Data Processing

7.2.1. Convention of data processing and processing of missing data

The missing dates of AEs or concomitant medications/treatments will be imputed as follows. The imputation of missing dates will be used for classification only. When tabulations of relevant data are generated, unimputed dates will be still presented.

Missing of start date:

- 1) If the year and month are known and both are earlier than those of the first dose of the investigational product, the last day of the known month will be used for imputation.
- 2) If the year and month are known and same as those of the first dose of the investigational product, the start date is the date of the first dose of the investigational product (date refers to “month, day”).
- 3) If the year and month are known and later than those of the first dose of the investigational product, it will be imputed with the first day of the known month.
- 4) If only the year is known and earlier than that of the first dose of the investigational product, “December 31” will be used for imputation.
- 5) If only the year is known and same as that of the first dose of the investigational product, the start date is the date of the first dose of the investigational product (date refers to “month, day”).
- 6) If only the year is known and later than that of the first dose of the investigational product, it will be imputed with “January 1”.
- 7) In other situations, the date of the first dose of the investigational product will be taken as corresponding start date.

Missing of end date:

- 1) If the year and month are known, it will be imputed with the last day of the known month.
- 2) If only the year is known, it will be imputed with “December 31”.
- 3) If the end date imputed is earlier than the start date, the end date will be taken as corresponding start date.
- 4) Other conditions are regarded as missing.

Missing laboratory data, ECG data, vital signs data, physical examination and other safety data will not be imputed.

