12.11. Data Convention

If the start date of an AE or concomitant medication is incomplete or missing, it is assumed that the AE has occurred during or after the use of the study drug, unless the incomplete date (e.g., month and year) clearly shows that the event began before treatment. If part of the date indicates the same month or year as the study drug use date, the start date of the AE is imputed according to the study drug use date. Otherwise, the missing day or month is imputed according to the first day or month.

Missing laboratory data, ECG data, vital signs data, physical examination and other safety data will not be imputed.

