4.2.2. Adverse events (AEs)

AEs

An adverse event refers to any untoward medical occurrence after subjects receive the investigational medicinal product, which can be manifested as symptoms, signs, diseases or laboratory test abnormalities, but are not necessarily related to the investigational medicinal product. See Section 10.1 of the protocol for details.

Treatment-emergent adverse event (TEAE)

TEAE is defined as an AE that occurs or worsens during treatment. The treatment period refers to the period from the first study drug administration to the end of the protocol-specified follow-up period. The cut-off date of TEAEs in Stage 1 is immediately before the first dose for Stage 2 or 10 weeks (70 days) after end of dosing in Stage 1, whichever occurs first; for the subjects who discontinue administration in Stage 1, the cut-off date of TEAEs is the end of follow-up period. TEAEs in Stage 2 is from the end of the first dose for Stage 2 to the end of the follow-up period.

Drug-related AEs

A drug-related AE refers to an AE whose relationship with the drug is related, possibly related or indeterminable.

The criteria for determination of the correlation of AEs with treatment are as follows:

Correlation	Criteria for determination
Related	
There is a reasonable temporal sequence between the occurrence of AE and the medication;The study drug explains the AE more reasonably than other reasons (e.g., the patient's preexisting disease, environmental or toxic factors, or other treatments the patient received, etc.);The AE disappears or lessens after the drug is stopped or the dose is reduced;The AE meets the known AE types of the suspect drug or its similar drugs;The AE recurs after re-administration.
Possibly related	
There is a reasonable temporal sequence between the occurrence of AE and the medication;The study drug explains the AE as reasonably as other reasons (e.g., the patient's preexisting disease, environmental or toxic factors, or other treatments the patient received, etc.);The AE disappears or lessens after the drug is stopped or the dose is reduced (if applicable).
Unlikely related	
Other reasons (e.g., the patient's preexisting disease, environmental or toxic

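### Partial AE start dates have no anchor at first CBP-201 exposure, so some partly dated AEs in placebo starters that may follow the W16 dose are counted as placebo AEs

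*SAP*

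**What the plan says.** SAP 7.2.1 lists seven rules for missing start dates, all tied to the first dose of the investigational product. None mentions the first Stage 2 dose.

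- Rule 2, "If the year and month are known and same as those of the first dose of the investigational product": the start becomes the date of that dose.
- Rule 3: "If the year and month are known and later than those of the first dose of the investigational product, it will be imputed", and the day used is the 1st of that month.
- Rule 5, "If only the year is known and same as that of the first dose of the investigational product": again the first-dose date. Rule 6 sends a later year to 1 January.
- Rule 7, the fallback: "In other situations, the date of the first dose of the investigational product will be taken as corresponding start date".

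The section adds: "The imputation of missing dates will be used for classification only". Classification is where the gap appears. SAP 4.2.2 ends the Stage 1 TEAE period just before the first Stage 2 dose, or 70 days after Stage 1 dosing ends if that is sooner, and then states "TEAEs in Stage 2 is from the end of the first dose for Stage 2 to the end of the follow-up period". SAP Table 4 starts the SS2 period at the first Stage 2 dose and the SS3 period at the first CBP-201 dose.

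Protocol 12.11 says of an incomplete start date that "it is assumed that the AE has occurred during or after the use of the study drug", unless the known part shows onset before treatment. It then uses the study drug date if the month or year matches, and otherwise the first day or month. It names no stage.

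**The concern.** The imputation uses one reference date, but the safety analyses use two boundaries. Every Stage 2 group receives CBP-201 at W16 (Protocol Table 6.2), so for a subject randomised to placebo the second boundary is first exposure to the drug. A partial date resolved against Day 1 alone can put an AE that followed this exposure into placebo time. The placebo column of SS1 then gains an event, and the SS2 counts, the SS3 counts and the SS3 annual incidences (SAP 7.5.2) lose it.

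This looks like a carry-over. The same start-date rules stand in SAP version 1.0, section 7.2.1, a plan written mainly for Stage 1. The current SAP added the Stage 2 TEAE period, SS2 and SS3 without changing them, and SAP 7.8 does not mention the point.

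**Working it through.** The plan states no figure on this point, so there is none to reproduce. The check applies the rules to dates, taking Day 1 as the reference dose.

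**Inputs.** W16 is D113 ±3 days, that is, Day 1 plus 109 to 115 days; follow-up ends at D421, Day 1 plus 420 (Protocol Table 1.2). Rules are from SAP 7.2.1, boundaries from SAP 4.2.2 and Table 4. Assumption: Day 1 dates and true onset days are uniform, because the documents give no AE rates and no count of partial dates. Day 1 was run over 1,461 consecutive dates (four calendar years).

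**Step 1: which rule governs the W16 month.** A gap of at least 109 days cannot fit within one calendar month. Day 1 and W16 shared a month for 0 of 1,461 dates at each offset. So rule 2 never applies to the W16 month and rule 3 always does.

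**Step 2: illustration.** Day 1 on 26 January 2022 gives W16 on 18 May 2022 (+112 days). An AE dated only May 2022 is set to 1 May, 17 days before the dose, hence Stage 1.

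**Step 3: unknown day in the W16 month.** With the dose on day d of a month of length L, that month has L − d + 1 Stage 2 onset days. All are imputed before the dose unless d = 1.

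- Stage 2 onset days in the W16 month: 22,981.
- Moved to Stage 1: 21,520, and 21,520 / 22,981 = 93.6%.
- Dose on the 1st, giving a same-day tie: 1,461, or 6.4%. The SAP does not say how a date-only tie is resolved.

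**Step 4: share of all Stage 2 onset days.**

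| W16 offset | All Stage 2 onset days | Moved, day unknown | Moved, only year known |
|---|---|---|---|
| +109 | 455,832 | 21,520 / 455,832 = 4.7% | 57.2% |
| +112 | 451,449 | 21,520 / 451,449 = 4.8% | 57.6% |
| +115 | 447,066 | 21,520 / 447,066 = 4.8% | 58.0% |

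A fully missing start date always goes to Day 1 under rule 7.

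**Step 5: where the moved AE lands.**

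- Randomised to placebo: counted under placebo in SS1, absent from SS2 and SS3.
- Randomised to CBP-201: counted under CBP-201 in SS1, absent from SS2, still in SS3.

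**Step 6: the opposite error.** The same month has d − 1 Stage 1 days. Summed over d = 1 to L this is L(L − 1)/2. The Stage 2 days moved under rule 3 sum to L(L + 1)/2 − L = L(L − 1)/2, the same number. An anchor at W16 with no other condition would therefore misplace as many Stage 1 onset days in that month (21,520) as rule 3 now misplaces Stage 2 days.

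**The case against.** Four arguments carry weight.

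1. **The protocol is not contradicted.** A reader might infer that the SAP reverses a conservative protocol rule. It does not. Protocol 12.11 speaks of study drug, which includes placebo, has no stage anchor, and itself falls back to the first day or month. This stands.
2. **The shift is not always away from CBP-201.** A reader might infer that it is. Randomisation is 2:1, and for the larger arm the AE stays on CBP-201, stays in SS3 and adds to the CBP-201 column of SS1. This stands; the misattribution concerns placebo starters only.
3. **Few records, and not the feared ones.** AEs are collected at two-weekly visits and start date is an AE-page field (Protocol 10.4.1). A reader might infer that early hypersensitivity or injection reactions would be lost. The documents do not support that: immediate hypersensitivity is defined by onset within minutes to hours (Protocol 10.4.3), subjects are monitored for 2 hours after dosing at W16, W18 and W20, and injection sites are checked before leaving and at the next visit. Listings show unimputed dates, and Stage 2 has no formal inference. This limits the size but does not remove the error.
4. **A W16 anchor trades one error for an equal one.** Step 6 confirms this for an unconditional anchor. It argues for restricting the anchor to placebo starters and for using any known end date. It does not justify leaving the error in the direction that favours the drug.

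The term investigational product could also mean CBP-201 only, since SAP 3.1 sets it against placebo. Then a switcher's reference would be W16 and rule 2 would place the AE correctly. That reading is unlikely: version 1.0 used the same rules for Stage 1, when placebo subjects had no CBP-201 dose. The term still needs a definition.

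**Conclusion.** The point holds as a small, systematic misclassification in the safety tabulations. For placebo starters entering Stage 2, the written rules place AEs with unknown day in the W16 month, and many year-only or undated AEs, before first CBP-201 exposure even when they may follow it.

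The percentages are shares of onset days under uniform onset and a Day 1 reference, not shares of recorded AEs. The absolute effect cannot be computed without a count of partial dates. A reader might take the 72 placebo subjects in Protocol 12.3 as the number who switch; that is a design figure for completers after an assumed 15% dropout, not a count entering Stage 2. Efficacy results are untouched. The matter is minor, but cheap to correct.

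**What to change.** In SAP 7.2.1:

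- Define the first dose of the investigational product, stating whether a Day 1 placebo dose counts.
- Add a rule for subjects randomised to placebo who later receive CBP-201. If the known part of an AE start date is compatible with onset on or after the first CBP-201 dose (W16), the existing rules would place it earlier, and no known end date precedes that dose, impute the date of that dose. Months wholly after W16 stay under rule 3.
- Use this single imputed date for SS1, SS2 and SS3, so that no AE carries two start dates or is counted in both stages.
- Count a start date equal to the first Stage 2 dose date as Stage 2.

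The cost is a few sentences and a small change to the AE date derivation. SS1 tables already run under the existing rules may need a reconciling footnote. Some true placebo-period AEs with partial dates will be counted on CBP-201, which is the conservative direction.

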7.1. Inclusion Criteria

Patients must meet all of the following criteria to be enrolled into this study:

- 1) $12 \leq \text{age} \leq 75$ years at the screening visit, male or female; *note: the adolescent subjects aged <18 years should have body weight} \geq 40 \text{ kg.}*
- 2) Diagnosed with atopic dermatitis (according to the American Academy of Dermatology's Guidelines of care for the management of atopic dermatitis, 2014^[1]) at the time of screening, and:
 - a) The subject has been suffering from the disease for more than 1 year at the time of screening, and according to the judgment of the investigator, the subject has had poor response to topical drugs such as corticosteroids, phosphodiesterase-4 (PDE-4) inhibitors or calcineurin inhibitors (TCI), or it is not medically suitable for the subject to receive topical drug treatment (e.g., there are important side effects or safety risks);

Note: Poor response is defined as any of the following conditions:

- i. The patient has not achieved and maintained response or reached a low disease activity state (equivalent to IGA 0=asymptomatic to 2=mild) despite regular use of topical therapy during the 1 year before baseline;
- ii. The patient has received systemic treatment for AD despite regular use of topical therapy during the 1 year before baseline.

- b) At the screening and baseline visit, Investigator's Global Assessment (IGA) score ≥ 3 (according to the validated Investigator Global Assessment for Atopic Dermatitis [vIGA-AD™] scale, see [Section 17.4 Appendix D](#)), Eczema Area and Severity Index (EASI) score ≥ 16 (see [Section 17.5, Appendix E](#)), and $\geq 10\%$ body surface area (BSA) of AD involvement (see [Section 17.6, Appendix F](#));
- c) The average score of the maximum pruritus intensity in the Peak Pruritus Numerical Rating Scale (PP-NRS) ≥ 4 (see [Section 17.1, Appendix A](#)).

Note: The baseline average maximum pruritus PP-NRS intensity score will be calculated based on the average value of the maximum pruritus intensity PP-NRS score [daily score range 0-10] every day within 7 days before randomization. In these 7 days, the scores of at least 4 days are required for the calculation of the baseline average score. If the patient's reporting days are less than 4 days in the 7 days before the planned date of randomization, randomization should be postponed until the requirements are met, but it is not allowed to exceed the maximum screening period of 28 days.

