7.3.6. Prior medication, concomitant medication, and prior and concomitant non-drug therapies

The primary analysis will be performed based on RS1. Stage 2 analysis will be performed based on RS2 (only concomitant medications and treatments in Stage 2).

Prior and Concomitant Medications

Prior medication refers to a non-study drug that is started and ended before the first dose of study drug. Concomitant medication refers to a drug that is started at the time of or after the first dose of study drug, or a drug that is started before the first dose of the study drug and continued after the first dose of the study drug.

Prior and concomitant medications will be coded based on World Health Organization Drug Dictionary (WHODrug), and summarized based on ATC Level 2, ATC Level 4 (if the code is missing, it will be analyzed with the code of previous level) and PT. The number and percentage of subjects will be calculated. Prior and concomitant medications will be ranked in descending order of total number of subjects by ATC Level 2, ATC Level 4 and PT. In addition, they will be tabulated.

Prior and Concomitant Non-drug Therapies

Prior non-drug therapy refers to a therapy that is started and ended before the first dose of study drug. Concomitant non-drug therapy refers to a therapy that is started at the time of or after the first dose of study drug, or a therapy that is started before the first dose of the study drug and continued after the first dose of the study drug.

Prior and concomitant non-drug therapies will be coded by MedDRA. Concomitant non-drug therapies will be summarized by PT. The number and percentage of subjects will be calculated. Prior and concomitant non-drug therapies will be ranked in descending order of total number of subjects. They will be tabulated.

Rescue Treatment

Rescue treatments during treatment period of Stages 1 and 2 will be summarized based on ATC Level 2, ATC Level 4 (if the code is missing, it will be analyzed with the code of previous level) and PT. The number and percentage of subjects will be calculated. These rescue treatments will be ranked in descending order of total number of subjects by ATC Level 2, ATC Level 4 and PT. They will be tabulated.

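### The start-date imputation rules do not look at the end date, so some medications and adverse events that ended before the first dose are classed as concomitant or treatment-emergent

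*SAP*

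**What the plan says.** The later SAP version, section 7.2.1, gives seven rules for incomplete start dates and four for incomplete end dates of adverse events and concomitant medications or treatments. Their purpose is explicit: "The imputation of missing dates will be used for classification only". SAP version 1.0, section 7.2.1, has the same rules.

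Three start-date rules lead to the first-dose date:

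- Rule 2: "If the year and month are known and same as those of the first dose of the investigational product, the start date is" the first-dose date.
- Rule 5: "If only the year is known and same as that of the first dose of the investigational product, the start date is" the first-dose date.
- Rule 7, the catch-all, which covers a wholly missing start: "In other situations, the date of the first dose of the investigational product will be taken as corresponding start date".

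None of the seven mentions the end date. The only rule that compares the two dates is end-date rule 3: "If the end date imputed is earlier than the start date, the end date will be taken as corresponding start date".

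The classes are defined elsewhere. SAP 7.3.6 says "Prior medication refers to a non-study drug that is started and ended before the first dose of study drug" and "Concomitant medication refers to a drug that is started at the time of or after the first dose of study drug". SAP 4.2.2 opens the treatment-emergent period at the first administration of study drug.

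**The concern.** Setting an uncertain start to the first dose is a sensible default when nothing else is known. It fails when the end date already shows that the drug was stopped, or the event resolved, before dosing. The start must then also precede dosing, yet the rules place it on Day 1. Since classification is the only use of the imputed date, the rule fails at the one thing it is for.

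Such records can be expected. Protocol 9.2.3 records drugs taken in the 30 days before screening. Protocol 7.1 defines poor response by failure "despite regular use of topical therapy during the 1 year before baseline", and Protocol 7.2 excludes topical AD drugs within 2 weeks, and systemic immunosuppressants within 4 weeks, before baseline. Stop dates therefore matter for eligibility, while the start of a long-standing treatment may well be unknown. Protocol 10.4.1 collects adverse events from consent, so events that resolve before dosing can also be in the data.

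At stake are the concomitant-medication tables (SAP 7.3.6) and the treatment-emergent event tables (SAP 7.5.2). Whether the efficacy analysis is also exposed depends on how intercurrent events are flagged, which the SAP does not state.

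**Working it through.** The plan gives no figure to reproduce. The check applies the rules as written to test records, then repeats it with an end-date check.

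**Inputs.** Start-date rules 1 to 7 and end-date rules 1 to 4 come from SAP 7.2.1, and the class definitions from SAP 7.3.6 and 4.2.2. The first dose is assumed to be 20 March 2022, for illustration only.

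**Classification as written.** Imputed start on or after the first dose: concomitant or treatment-emergent. Start and end both before the first dose: prior or pre-treatment.

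**With the check.** If the known end, or the latest date that a partial end allows, is before the first dose: prior or pre-treatment.

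| Record | Start recorded | End recorded | Imputed start | End used | As written | With check |
|---|---|---|---|---|---|---|
| a | unknown | 10 Mar 2022 | 20 Mar 2022 (rule 7) | 10 Mar 2022 | concomitant / TEAE | prior / pre-treatment |
| b | Mar 2022 | 10 Mar 2022 | 20 Mar 2022 (rule 2) | 10 Mar 2022 | concomitant / TEAE | prior / pre-treatment |
| c | 2022 | 15 Feb 2022 | 20 Mar 2022 (rule 5) | 15 Feb 2022 | concomitant / TEAE | prior / pre-treatment |
| d | unknown | Feb 2022 | 20 Mar 2022 (rule 7) | 28 Feb, moved to 20 Mar 2022 (end rule 3) | concomitant / TEAE | prior / pre-treatment |
| e | unknown | 2021 | 20 Mar 2022 (rule 7) | 31 Dec 2021, moved to 20 Mar 2022 (end rule 3) | concomitant / TEAE | prior / pre-treatment |
| f | Feb 2022 | 10 Feb 2022 | 28 Feb 2022 (rule 1) | 10 Feb 2022 | prior / pre-treatment | prior / pre-treatment |
| g | 2021 | 10 Mar 2022 | 31 Dec 2021 (rule 4) | 10 Mar 2022 | prior / pre-treatment | prior / pre-treatment |

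All five records caught by rule 2, 5 or 7 are misclassified, and the check corrects all five. The two handled by rules 1 and 4 already have the right class, although record f also has an imputed start after its end.

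**Complete end date (a to c).** The start falls after the end, by 10 days in a and b. Nothing resolves this, because end-date rule 3 concerns only an imputed end.

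**Partial end date (d and e).** The table reads end-date rule 3 as moving the end forward to the start. Its wording is ambiguous: it shares its closing phrase with start-date rule 7, where the phrase assigns a start date. Read that way, the start would move back to the end (28 Feb 2022 in d, 31 Dec 2021 in e), and both records would be prior. Even on the table's reading, rule 3 does not worsen the class, since rule 7 has already put the start on Day 1. Records a to c do not depend on the reading.

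**Intercurrent events (SAP 7.4.2).** Take a topical steroid falsely placed on Day 1.

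- Its duration is at most 1 day, against the limit of 7.
- W16 is Day 113, so its end is at least 113 − 1 = 112 days (16 weeks) before W16, against the required 4 weeks.
- By itself it is event 2: treatment policy, observed value used.

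A mandatory-stop drug, such as a systemic steroid, has no minimum duration. Event 1 requires use because of poor response, which a drug stopped before dosing cannot show. Event 6 covers use for other reasons; it discards observed values and imputes by jump to reference.

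**The case against.** The strongest reply is that the SAP need not be applied mechanically. A drug with a known stop before Day 1 plainly meets the definition of prior medication, so a sensible programmer would never send it to the imputation rules. Tabulations show unimputed dates, and Protocol 12.11 adopts the same conservative default for incomplete starts. For adverse events, sites record pre-dose events as pre-treatment events, the case report form asks for a start date, and screening lasts at most 28 days, so affected events should be rare.

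Part of this stands. The adverse-event side is probably the smaller one, and an attentive programmer may avoid the error. But the SAP states no such step and does not say that the site's pre-treatment label overrides the imputed date. The exception in Protocol 12.11 looks only at the incomplete date itself. Unimputed dates in a listing do not correct the class used in a summary table.

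Three stronger inferences are not supported:

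- **That false Day 1 topical records would overturn W16 results.** By themselves they fall under event 2. For mandatory-stop drugs only event 6 is open, and the SAP does not say that events are flagged from imputed dates. Protocol 8.2.1 ties mandatory discontinuation to treatment begun after the first dose, and SAP section 6 says that major deviations affecting efficacy were settled at blinded data review meetings.
- **That every subject has a prior topical record.** Protocol 7.1 also admits patients for whom topical treatment is medically unsuitable.
- **That a percentage of affected subjects can be given.** It would need the share with a recorded prior topical and the share of those lacking a start date. The documents give neither.

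**Conclusion.** The point holds for records that ended before the first dose and whose start is caught by rule 2, 5 or 7. It is firm for complete end dates. For partial end dates it depends on how end-date rule 3 is read. Complete start dates, and partial starts in an earlier month or year, are classified correctly.

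The certain consequence of following the written rules is a wrong class in the concomitant-medication and treatment-emergent event summaries for each affected record. The number of such records is unknown. An efficacy consequence is conditional: it needs a mandatory-stop drug with this date pattern and flagging of event 6 from imputed dates. This is a modest defect, worth correcting because the correction costs so little.

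**What to change.** In SAP 7.2.1, before start-date rules 1 to 7, add: *If the known end date, or the latest date a partial end date allows, is before the first dose, classify the record as prior medication or pre-treatment AE and do not impute a start later than the end date.*

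Then:

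- Apply rules 2, 5 and 7 only when the end is missing, ongoing, or could fall on or after the first dose. The conservative default stays wherever timing is truly uncertain.
- Reword end-date rule 3 to say which date is changed, and restrict it so that it cannot move a pre-dose end to Day 1.
- State whether imputed dates are used to flag intercurrent events. If they are, use the same order there.

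The cost is a few sentences in the SAP and one condition in the programs. A listing of records whose class changes would show the size of the effect and whether any tables already produced need to be rerun.
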